2.1 Study Outcomes

Primary Outcome: A composite tolerability score based on 4 GI side effect profile categories over 1 week. **Secondary Outcome**: Stool SCFA content (proprionate and butyrate levels) after 1 week and 4 weeks of treatment. **Exploratory Outcomes**: Stool microbial diversity indices, stool metabolites (bile acid concentrations, lactic acid, hydrogen sulfide), serum markers of intestinal permeability; glucose, insulin, GLP-1 and PYY concentrations during a mixed meal test.

3.0 Study Design

3.1 Study Design and Timeline

This 9-week pilot study will have 2 phases and 6 outpatient visits at the NIH Clinical Center (Figure 4). Phase 1 is a 5week randomized double-blind randomized cross-over trial with two 1-week intervention periods (metformin + prebiotic and metformin + placebo). Phase 2 will occur immediately following phase 1 in which participants will start an openlabel 4-week intervention with metformin and the prebiotic MM.

Phase 1: This is a randomized double-blind cross-over study of youth with T2D with two intervention periods (metformin + prebiotic MM BiomeBliss® ®, and metformin + placebo). Participants will have 5 study visits over the 5-week period. After screening history and physical examination are performed at visit 1, participants will enter a 1-week run-in period in which metformin therapy will be discontinued and blood glucose will be monitored twice daily via finger stick or with a continuous glucose monitor. The order of intervention will be randomized at Visit 2; when initiating metformin, participants will have 1-3 days of dose escalation, then arrive at a final dose of 850mg twice daily. After 7-9 days of treatment, participants will be evaluated as described in Table 1, then enter a 2-week washout period of prebiotic/placebo and metformin, and then cross over to the opposite intervention for 1 week.

Phase 2: This is an open-label 4-week extension of metformin + prebiotic MM. Participants will receive a 1-month supply of metformin and prebiotic at the end of Phase 1 (Visit 5) and be evaluated for measures of stool metabolite and glycemia at the end of the trial (Visit 6).

Every effort will be made to adhere to the proposed timelines, but some flexibility is required for scheduling of other studies, unanticipated equipment maintenance, etc. Scheduling variations will not be reported.

3.2 Study Protocol

Table 1 illustrates study procedures and timing over the 2 study phases. All visits will take place at the NIH Hatfield Clinical Center. Except for the screening visit, participants will be evaluated after an 8-10 hour overnight fast. Detailed descriptions of each procedure/ visit are given below.

Table 1 – Study Procedures and timeline

	Visit 1	Run in (7-10 days)	Visit 2	Period 1 (7-9 days)	Visit 3	Wash out (2-3 weeks)	Visit 4	Period 2 (7-9 days)	Visit 5	Open Label (4 weeks)	Visit 6
Histories and Que	estionr	naires									
History/Physical	х		х		х		х		x		X
Quality of Life Questionnaire			х		x		х		x		x
Food Record Kept		х								х	
GI Symptom Questionnaire		Every 3 days		Daily		Every 3 days		Daily		Every 3 days	
Testing											
Mixed Meal Test and other blood tests					x				x		x
Urine Collection	х		Х		Х		х		x		Х
Stool sample collected			х		x		х		x		x
DXA			Х								
Daily CGM worn		Х		х		х		х		Х	
Accelerometer worn				х				х		х	
Study Agents											
Study Medications Given			х				Х		x		
Pill/Bottle count					X				x		X
Meals given from metabolic kitchen			Х				Х				

Subject Identification: potential participants will be referred by local providers responsible for clinical care. This includes the Children's National Multidisciplinary Type-2 Diabetes clinic, as well as from other community providers to whom we will provide information about our study (see recruitment strategies, 8.4). Interested participants will be given our study information and will contact us via the study line or email. Participants will be phone screened to determine

baseline eligibility and additional study information. If participants are eligible, we will arrange a screening visit at the NIH.

Screening visit (Visit 1): After initial screening for eligibility and informed consent process completed, participants will undergo history and physical examination, routine bloodwork, and urine test to determine eligibility. Nutrition staff will also obtain body circumference measures, such as neck, waist and hip circumference. These measurements will be done over minimal clothing with a non-stretch measuring tape.

Participants will receive instructions on stool collection at home and stool collection kits - one to be mailed back to the study team for analysis prior to stopping their baseline metformin dose (unless they are able to provide a stool sample after consent while still at NIH), and one to collect a sample in the 24 hours prior to visit 2 if has a bowel movement. Patients will also be taught how to fill out daily surveys to assess GI symptoms (see details below). They will meet with a member of the nutrition team to select foods for their metabolic diet and to be educated on completing a 3-day food record. Participants will also be educated on foods we will ask them to avoid during the study, such as pre/pro-biotics (kombucha, kefir, yogurt, etc.) and foods containing non-nutritive sweeteners.

Period 1 (Drug-free run-in, Visit 2 and 3)

Drug-free run-in period: Participants will discontinue metformin for the 7-10 days preceding Visit 2, to assess their metabolic and gut microbiome response off anti-diabetic medications, as well as to wash out the immediate effect of metformin on the participants microbiota. The timing of this 1 week period was chosen because changes in gut microbiome have been observed in as little as 1 day and on average 1 week [33]. During this time, participants will complete daily GI symptom questionnaires and monitor their blood glucose and upload their readings daily while not taking metformin. Participants with persistently elevated fasting glucose readings and/or signs and symptoms of metabolic decompensation (e.g. vomiting, dehydration, lethargy, abdominal pain, ketonuria and acidosis) will be withdrawn from the study and restarted on his/her medication. During the drug-free run-in period, individuals who cannot either wear the continuous glucose monitor (CGM), or complete at least 2 finger stick blood glucose measurements daily will be withdrawn from the study.

Visit 2: This visit will take place 7-10 days after discontinuing metformin. Study personnel will review dosing and the completeness of GI questionnaires, as well as glucose trends with the participants. Participants will leave with a study metformin supply from the NIH pharmacy, as well as bottles of either placebo or prebiotic for a 1 week +15% supply and be instructed to take metformin and the powder mixed with a shake provided by the study team at the same time twice daily, with the first dose given with dinner that evening. Participants will take metformin 850mg with dinner on day 1-3and the dose will be increased to 850mg with breakfast and with dinner on day 3 and thereafter. Participants will fill out daily GI symptom questionnaires and will be instructed to contact the NIH study team if they are unable to tolerate the medication. Participants will be provided with 1 week of food to take home and consume on the week prior to Visit 3. The NIH Clinical Center Metabolic Kitchen will pack out meals for 7 days. Energy provided will be estimated using Mifflin St Jeor equation and an activity factor of 1.3 [34]. Participants will also leave with an accelerometer to be worn around the wrist 24 hours/day during the period between visits 2 and 3.

Visit 3: Participants will return to the NIH CC 7-9 days after visit 2. Stool and urine sample collection and bottle/ pill counts and assessment of uneaten food will be performed, and the accelerometer will be returned. Participants will undergo a MMT (see description below). Completeness of GI symptom questionnaires and glucose trends will be reviewed.

Period 2 (Washout, Visit 4 and 5)

Participants will be instructed to stop taking all metformin and MM/placebo powder during the washout period between visit 3 and 4; instructions for CGM and hyperglycemia precautions that were given at the screening visit will be reviewed with the family. The 2-3 week washout was chosen to minimize any carry-over effects and has been optimal for detecting gut microbiota after discontinuing therapy [9, 27].

Visit 4: Visit 4 will occur at the NIH CC 14-24 days after the beginning of the wash out period; The NIH Clinical Center Metabolic Kitchen will pack out frozen and non-perishable items to provide meals for 7 days. Participants will also be asked to wear the accelerometer on wrist until they return for visit 5.

Visit 5: Participants will bring a stool sample and study medications and have identical assessments as described in visit 3 above. They will also be reminded about keeping food records, which they will be asked to do prior to visit 6

Phase 2 (open-label study and Visit 6)

At the end of Visit 5, patients will leave with a 1-month supply of metformin and MM, to continue taking twice daily, as well as an accelerometer device daily for 4 weeks. **Final study Visit 6** – Participants will undergo assessments as outlined in Table 1 and receive counseling on resuming their medication regimen from prior to the study, as well as follow up nutrition counseling on healthy diet and lifestyle practices.

Rescue visit for GI intolerance

If participants are unable to tolerate 850mg twice daily during the study, they will be withdrawn from the study and have the option come in for a rescue visit, where they will provide a stool sample and obtain bloodwork. They will then be offered the opportunity to enter the open label arm using BiomeBliss® in combination with their highest tolerable metformin dose.

3.2.1 Study Procedures

- **GI symptom questionnaires**: A questionnaire derived from validated sets used for GI symptoms of irritable bowel syndrome [35] which previous investigators have used [27]. Assessments of stool consistency (not applicable, very hard, hard, formed, loose, watery), urgency to evacuate (no need to evacuate within 3 hours after dosing, need to evacuate within 3 hours, need to evacuate within 2 hours, need to evacuate within 1 hour), daily bowel movements (at least 1 movement every 3-4 days, at least 1 movement every 2 days, at least 1 movement per day, at least 2 movements per day), bloating sensation (not applicable, mild, moderate, severe), flatulence (less than normal, normal, moderately increased, greatly increased), and evacuation completeness (not applicable, incomplete, constipated), in addition to a King's stool chart, will be included (see Appendix A) [27]. This survey will be available in an online platform designed for mobile device but may also be filled out in paper form.
- **Blood glucose monitoring**: Blood glucose will be monitored with either fingerstick blood glucose twice daily (fasting and bedtime) or by using an FDA- approved continuous glucose monitoring device (CGM) (for example, the Freestyle Libre). The device will be used to monitor glucose in real-time, approximately every 5 minutes. The system consists of a small sensor, transmitter, and hand-held receiver. The small sensor, with a small needle attached, will be inserted subcutaneously. The transmitter, which is attached to the sensor, will send the measured glucose to the receiver. The sensor is changed at least once every two weeks. Participants will receive training on removing and replacing the sensor and education on the signs and symptoms of hyperglycemia (see Appendix B). Participants will be asked to upload their readings daily to be monitored by a member of the study team daily while participants are not taking metformin, and weekly while taking metformin. Participants will be asked to contact the study team immediately after confirming with a finger stick BG if their glucose is low (<50mg/dL), or if they have a fasting blood glucose reading of >200mg/dl, or a reading anytime of >300mg/dl. Participants with persistently elevated fasting glucose readings and/or signs and symptoms of metabolic decompensation (e.g. vomiting, dehydration, lethargy, abdominal pain, ketonuria and acidosis) will be withdrawn from the study and restarted on his/her medication.

- Activity and Sleep Monitoring: Free-living physical activity and sleep quality will be quantified using a small, non-invasive, portable watch accelerometer (GT3X+ by Actigraph Inc., Pensacola FL) worn on the participant's wrist. Physical activity levels, sleep duration and efficiency, amount of time spent in sedentary, moderate, vigorous intensity categories and estimated activity-associated energy expenditures will be extracted using established predictive equations. This is an FDA 510(k) cleared Class II medical device.
- Urine sample collection: urine will be collected at every visit for storage; for females, this same sample will be used for a pregnancy test
- **Stool sample collection:** Participants will bring stool samples from home collected in the previous 24 hours to be processed by the study team or stool samples will be collected during outpatient visits. The stool sample will be stored at 4C in a sterile plastic vial and processed same day (see Appendix C).
- Mixed Meal Test (MMT): One intravenous catheter will be placed in the arm for blood draws upon arrival on the morning of the MMT.A liquid meal to provide ~30% of the estimated daily calorie requirements for weight maintenance determined by the Mifflin St. Jeor equation with an activity factor of 1.3 [34]. Blood samples will be obtained at 0, 10, 20, 30, 40. 50, 60, 90, 120, 150 and 180 minutes to measure hormones and metabolites including glucose, lactate, free fatty acid, triglyceride, C-peptide, and insulin concentrations. Blood to measure markers of intestinal permeability will be obtained at time 0.
- **Quality of Life Questionnaire**: Participants will fill out the PedsQL quality of life questionnaire [32] (see Appendix D).
- **Food Records:** Participants will review their food records with a member of the nutrition team. If participants do not bring records to this appointment, the nutrition team will perform a 24-hour recall capturing foods consumed in the day prior to admission (see Appendix E).
- **DXA scan** dual x-ray absorptiometry scan will be performed to evaluate body composition and determine fat mass and lean body mass.

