1.0 Background

Metformin is the most widely prescribed anti-diabetic agent in the world and is first line for treatment of type 2 diabetes (T2D) in both adults and children [1, 2]. However, metformin non-responsiveness is an important clinical challenge, occurring in 20-50% of youth and adults [3], and reduced treatment adherence is a well-recognized and potentially modifiable risk factor [4]. Metformin related gastrointestinal (GI) side effects (bloating, diarrhea, cramping, nausea and

[figure not shown]

[figure not shown]
Figure 1Potential mechanisms of metformin-related changes in gut metabolites and lower GI side effects. H2S: hydrogen sulfide, GLP-1: glucagon-like peptide 1,FXR: farnesoid X receptor (References: 14-16)

vomiting) are a common barrier to maximal dose escalation and treatment optimization [5]. These side effects are also a frequently reported reason for non-adherence [5]. Side effects are observed in > 80% of individuals newly initiated on metformin and ~10-30% of patients on long-term therapy [6, 7], with estimates of 1 in 4 youth taking metformin having at least one GI side effect [8]. Challenges are magnified in youth with T2D, as metformin is the only oral medication that is approved for use in the 10-17-year age group. Yet, there is a paucity of studies examining the mechanisms of metformin's GI side effects in vivo, and thus limited ability to mitigate these

Last updated: February 9, 2021

issues. This pilot study, a randomized double-blind crossover trial, examines the use of a prebiotic as an adjunct to improving metformin tolerability, facilitating short-term dose escalation, and also explores the underlying gut-based mechanisms of both metformin action and intolerance in youth and young adults with type 2 diabetes.

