3.5.1 Dose titration for gastrointestinal intolerance

13g

Non-fiber

Carbohydrate

At the start of each period, participants will take metformin 850mg daily, regardless of their dose prior to beginning the study. Participants will be titrated up to 850mg twice daily within 1-3days of Period 1 and 2. For participants who experience intolerable gastrointestinal side effects, metformin dose will be decreased by 850mg. Examples of such side effects include 3 or more diarrheal episodes or intense discomfort or cramping for more than 3 hours. If gastrointestinal symptoms resolve x 2 days, and at the discretion of the PI, the dose of metformin may be increased again to 850mg twice daily. Participants who are unable to tolerate 850mg daily will come for the rescue visit and be withdrawn from the study.

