5.2 Analysis of Primary and Secondary Outcomes

The primary outcome, the participant's composite score of tolerability will be constructed using the principal component analysis (PCA) based on 4 GI side effect profile categories (stool consistency, urgency to evacuate, bloating sensation, and flatulence). PCA will be used to account for the expected high inter-patient variability. Comparison of mean tolerability score over 1 week will be with linear mixed models, adjusting for baseline score. Pre-specified covariates are: treatment period and sequence effects from the cross-over design.

The secondary outcome, change in mean stool SCFA over 1 and 4 weeks, will be analyzed using repeated measures of analysis variance (ANOVA) to consider correlation of observations within each participant. Participant and exploratory characteristics will be expressed as mean and standard deviation, median and interquartile range for continuous variables and frequency for categorical variables. Between group comparison of means will also be analyzed using repeated measures ANOVA. Spearman correlations will be used to compare relationships between continuous variables. A P-value of <0.05 will be used for statistical significance.

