8.5.2 Evaluation of Risks

This research protocol will be associated with greater than minimal risk. The specific risks and our approach to minimize these risks are outlined below.

- Blood Sampling: Peripheral blood draws (venipuncture) performed during this study for research will not exceed 10.5 mL/kg, or 550 mL (whichever is smaller) per 8-week period for adults. For pediatric patients, blood draws will not exceed 5 mL/kg in a single day, or 9.5 mL/kg or 550 mL (whichever is smaller) per 8-week period. The total blood volume for this study is 372 ml over the 9-week period. Patients may experience some discomfort at the site of the needle entry, and there is a risk of bruising at the site. There is a remote risk of fainting or local infection.
- 2. Intravenous Catheter Placement: The placement of intravenous catheters can be uncomfortable and pose the potential risk of bleeding, bruising and infection. All catheters will be placed under sterile conditions and universal precautions will be observed. Should any complications occur, they will be addressed immediately.

3. Risk associated with metformin

- i. Gastrointestinal upset: Nausea, vomiting, diarrhea, flatulence, abdominal discomfort and indigestion are common side effects associated with metformin use. To be eligible for this study, participants will have an indication to start metformin as first line therapy for type 2 diabetes, if they are not already taking it prior to the start of the study. The following actions will be taken to minimize the risk for gastrointestinal disturbance:
 - a. Metformin dosing will be dose escalated over a 1-3-day time period
 - b. Gastrointestinal symptoms will be recorded daily by participants and communicated with the study team with each submission of the online questionnaire.
 - c. Participants who experience severe and/or recurrent gastrointestinal symptoms, defined as ≥ 3 diarrheal episodes or intense discomfort or cramping > 3 hours, will be withdrawn from the study.
- ii. Boxed Warning Lactic acidosis (rare): The risk of lactic acidosis with metformin use is increased in elderly individuals with renal dysfunction or congenital heart failure. Participants with chronic renal or heart failure, or other chronic metabolic illnesses will not be recruited for this study.

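### The listed daily GI items do not ask about cramping or discomfort and cannot count three or more stools in a day, although the protocol acts on both events

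*Combined protocol and SAP*

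**What the plan says.** Section 3.2.1 describes a questionnaire with six items: stool consistency, urgency, number of bowel movements, bloating, flatulence and completeness of evacuation. The first item and the start of the second read "stool consistency (not applicable, very hard, hard, formed, loose, watery), urgency to evacuate". The upper end of the frequency scale and the bloating item after it read "at least 1 movement per day, at least 2 movements per day), bloating sensation (not applicable, mild, moderate, severe". A stool chart belongs to the same survey: "in addition to a King's stool chart, will be included (see Appendix A". Table 1 has the questionnaire completed daily in the two intervention periods and every 3 days in the other phases.

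Section 8.5.2 gives this as one of its measures to limit GI disturbance from metformin: "Gastrointestinal symptoms will be recorded daily by participants and communicated with the study team with each submission of the online questionnaire". Section 3.5.1 lowers the metformin dose for intolerable symptoms and illustrates them: "Examples of such side effects include 3 or more diarrheal episodes or intense discomfort or cramping for more than 3 hours". Sections 8.5.2 and 9.3.1 use the same two events as grounds for withdrawal.

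Section 5.2 forms the primary outcome by principal component analysis, "based on 4 GI side effect profile categories (stool consistency, urgency to evacuate, bloating sensation, and flatulence". The opening summary counts abdominal discomfort and cramping among the most common side effects of metformin, and Section 1.0 gives a similar list: "Metformin related gastrointestinal (GI) side effects (bloating, diarrhea, cramping, nausea and" vomiting.

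**The concern.** The form that is meant to carry GI symptoms to the study team does not, in its listed items, ask about one of the two events on which the protocol acts, and it cannot count the other within a day. Two things are at stake.

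- **Monitoring.** Participants may be as young as 10. One with hours of cramping but formed stool and little gas could return a form that looks close to normal. The event would then reach the team only if someone raised it by another route.
- **What the trial can say about tolerability.** The composite has no input for cramping or discomfort. If the prebiotic eased or worsened them, the primary score would have no direct way to show it, and no other structured daily measure is listed from which to describe it by powder.

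**Working it through.** No figure in the plan bears on this point and no sample size or power calculation enters it. The check sets the listed items beside the events and the composite.

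**Step 1. Events against the six listed items (Section 3.2.1).**

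| Event acted on (3.5.1, 8.5.2, 9.3.1) | Closest listed item | Can the event be read from it? |
|---|---|---|
| Strong cramping or discomfort, over 3 hours | None; bloating has a severity scale but no duration | No |
| Three or more diarrheal episodes | Frequency, consistency, urgency | Loose or watery stool: yes. Number of episodes in a day: no |

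Items that ask about cramping or discomfort: 0 of 6. Items that ask how long a symptom lasted: 0 of 6.

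**Step 2. The frequency scale.** Mapping a day's number of movements to the answer: 1 gives the category for at least one; 2, 3, 4, 5 and 6 all give the top category. The scale therefore cannot separate 2, which is below the event threshold, from 3 or more, which meets it.

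**Step 3. The time window.** None of the three sections says over what period the episodes are counted. If they are counted within one day, Step 2 applies and the listed items cannot show the event. If they accumulate over several days, three daily entries of loose or watery stool could show it. The gap in counting is firm only on the first reading.

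**Step 4. The composite (Section 5.2).** Inputs: consistency, urgency, bloating, flatulence.

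- Measure cramping or discomfort: 0 of 4.
- Count episodes: 0 of 4.
- Reflect diarrhea indirectly: 2 of 4 (consistency and urgency).

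Bowel frequency is not an input, so the ceiling in Step 2 matters for monitoring and does not touch the primary score.

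**Step 5. Other routes to the same information.** Participants are told at Visit 2 to contact the team if they cannot tolerate the medication (Section 3.2). All adverse events are recorded (Section 9.1). History and physical examination take place at Visits 3 and 5, at the end of each intervention period (Table 1). A research nurse outside the blind can speak with participants about problems with the powder (Section 3.5). These routes depend on spontaneous report or on recall at the end of a period, and none yields a daily graded measure that can be compared between powders.

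**The case against.** The strongest reply has four parts.

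**The form has not been seen in full.** The King's stool chart belongs to the same survey and may record each stool, and Appendix A was not available for this check. A reader might infer that the questionnaire cannot register these events at all. The documents do not support that for diarrhea, and for cramping they show only that nothing in Section 3.2.1 asks about it.

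**Safety does not hang on the form alone.** No section says that dose reduction or withdrawal is read off questionnaire answers, and several other routes exist. It would be wrong to conclude that the safeguard fails, or that participant contact is the only alternative. What stands is that the protocol names the form as a risk-limiting step while its listed items omit what the step after it in Section 8.5.2 acts on.

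**The primary outcome does reflect diarrhea.** Loose and watery stool and urgency are in the composite, so fewer diarrheal episodes would plausibly move two of its four inputs. A reader might infer that the score misses diarrhea, or that the frequency ceiling weakens it. Neither follows. Some discomfort may also be reported as bloating, although the opening summary lists the two separately.

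**The scope is lower GI effects, with items taken from earlier work.** Section 2.0 limits the aim to lower GI side effects and stool consistency, so the absence of nausea and vomiting is no fault in the score. Keeping the earlier adult study's items is defensible in a pilot, since Section 5.1 draws its planning values from that study. That supports leaving the composite alone. It does not explain why cramping goes unrecorded on the daily form.

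The 50% attrition in Section 5.1 might also be read as a sign that intolerance events will be common. The plan does not attribute it to intolerance, and Section 8.4.1 cites poor retention in youth trials generally.

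**Conclusion.** The point holds in a limited form. Among the listed items, none measures cramping or discomfort or its duration, and the frequency item cannot tell two movements in a day from three or more. The composite has no direct measure of either event and reflects diarrhea through two of its four inputs. The consequence is a gap in structured daily recording of symptoms that the protocol itself treats as intolerance; it does not invalidate the primary analysis, and nothing here shows that events would go unnoticed.

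The conclusion rests on two assumptions: that Appendix A adds no relevant item beyond those described in Section 3.2.1, and, for the count only, that episodes are meant to be counted within a day. The change is recommended because it is cheap and improves both monitoring and the description of tolerability.

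**What to change.** 1. Check Appendix A, including the King's stool chart. Unless already covered, add to the daily form:
   - the number of loose or watery stools in the past 24 hours, as a count;
   - abdominal cramping or discomfort: severity (none, mild, moderate, severe) and hours.
   - Optionally, nausea and vomiting, for monitoring only.
2. Set the online form to flag to the team any entry that meets the events already stated in Sections 3.5.1, 8.5.2 and 9.3.1. The protocol must state the period over which episodes are counted for this to work. In phases where the form is completed every 3 days, a 24-hour item covers only part of the interval, and the form should say so.
3. Report the new items by powder as supplementary outcomes beside the primary score. Leave the four-input composite as it is.
4. Separately, reconcile what follows from these events. Section 3.5.1 reduces the dose and withdraws only those who cannot tolerate 850 mg daily; the rescue-visit text in Section 3.2 withdraws those who cannot tolerate 850 mg twice daily; Sections 8.5.2 and 9.3.1 withdraw on the events themselves. This review takes no view on which rule is right.

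The cost is a few more questions on an existing mobile survey, a small added burden for participants, and an amendment to the protocol and Appendix A. No visit is added and no clinical rule needs to change for items 1 and 3.
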